7.5 Early study termination

The study can be terminated at any time for any reason by Novartis. Should this be necessary, subjects should be seen as soon as possible and treated as a prematurely withdrawn subject. The investigator may be informed of additional procedures to be followed in order to ensure that adequate consideration is given to the protection of the subject's interests.

The investigator will be responsible for informing IRBs/IECs of the early termination of the trial.

8 Procedures and assessments

Table 8-1 Assessment Schedule, Part 1

Enoch		Soroo	nina													Troo	tment									\neg
Epoch		Scree																								
Study Phase			Ba	selin	ie			1	1							Trea	tment									
Visit numbers (internal use only)	1	2		3	3		101	102	103				10	04			105	106	107				108	; 		
Visit name (internal use only)	Screening	Day -2		Day	y -1		Day 1	Day 2	Day 3				Da	y 4			Day 5	Day 6	Day 7				Day	8		
Study Day(s)	-28 to -2	-2		-	1		1	2	3				4	4			5	6	7				8			
Time (post-dose)	-	-	0h	4h	8h	12h	-	-	-	0h	1h	ı 2h	3	h 4h	8h	12h	-	-	-	0h	1h	2ľ	3h	4h	8h	12h
Informed consent	Χ																									
Inclusion / Exclusion criteria	Χ	Х																								
Study drug administration							Χ	Χ	Х	Χ							X	Χ	Χ	Χ						
Subjects domiciled														Χ												
Medical history/current medical conditions	Χ																									
Demography	Х																									
Body height	Х																									
Body weight	Χ																									
Vital Signs	Χ	Х	Χ				Χ	Χ	Х	Χ							X	Χ	Χ	Χ						
Physical examination	Χ	Х																								
Hepatitis and HIV Screen	Χ																									
Alcohol Test, Drug Screen, and Cotinine Test	Х																									
ECG evaluation	Χ	Х																								
Hematology	Χ		Х														Х									

Epoch		Scree	nin	g												Treat	ment									
Study Phase	Screening		Ва	seli	ne											Treat	ment									
Visit numbers (internal use only)	1	2			3		101	102	103				10	4			105	106	107				108	3		
Visit name (internal use only)	Screening	Day -2		Da	ay -1		Day 1	Day 2	Day 3				Day	i 4			Day 5	Day 6	Day 7				Day	8		
Study Day(s)	-28 to -2	-2			-1		1	2	3				4				5	6	7				8			
Time (post-dose)	-	-	0h	4h	8h	12h	-	-	-	0h	1h	2h	3h	4h	8h	12h	-	-	-	0h	1h	2h	3h	4h	8h	12h
Blood chemistry ²	Х		Χ				Х	X	Х	Χ							Х	Х	Х	Х						
Urinalysis	X		Х				X										X									
Urine albumin:creatinine ratio ³			Х				Х										Х									
Corporate Confidential Information			Х														Х									

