 $^{^{\}rm 6}$ PK blood samples obtained at 0h will be pre-dose samples on Days 4, 8 and 12

⁷ Pre-dose

⁹ Assessments on Study Days 1-3, 5-7, and 9-11 should be done pre-dose.

Table 8-2 Assessment schedule Part 2, Patients 1-16

Epoch	Scree	ning													Treatr	nent									
Study Phase	Screening	Baseline											Т	reatme	nt									Study Completion	30 Day safety follow up call
Visit Numbers ¹	V1	V2 ²	V3	V3.1	V3.2				V3.	3			V3.4	V3.5	V4 ³	V5	V6			\	/7			V777	n/a
Visit numbers (internal use only)	1	4	201	201.1	201.2	2			201.	.3			201.4	201.5	202	203	204			2	05			299	
Visit name (internal use only)	Screening	Day -1	Day 1	Day 2	Day 3			I	Day	4			Day 5	Day 6	Day 7	Day 14	Day 21			Da	y 28			End of study	
Study Day(s)	-28 to -4	-1	1	2	3				4				5	6	7	14	21			2	28			35	65
Study Day(s)	-20 10 -4	-1													-1 +1	-1 +1	-1 +1			-1	+0			-1 +2	
Time (post-dose)	-	0h	-			0h	1h	2h	3h	4h	8h	12h			-	-	-	0h	1h	2h	3h	4h	8h	-	
Informed consent	Х																								
Inclusion / Exclusion criteria	Х	х																							
Dose administration ⁴														Х											
Domicile								Χ																	
Medical history/current medical conditions	×																								
Demography	Х																								
Body height	Х																								
Body weight	Х																								
Hepatitis and HIV Screen	Х																								
Vital Signs	Х	Х	Х	Х	Х				Χ				Х	Х	Χ	Χ	Х	Х						Х	
Physical	Χ	Х																Х						Х	

Epoch	Scree	ning													Treatr	nent									
Study Phase	Screening												Т	reatme										Study Completion	30 Day safety follow up call
Visit Numbers ¹	V1	V2 ²	V3	V3.1	V3.2			,	V3.3	3			V3.4	V3.5	V4 ³	V5	V6			\	/7			V777	n/a
Visit numbers (internal use only)	1	4	201	201.1	201.2			2	201.	3			201.4	201.5	202	203	204			2	05			299	
Visit name (internal use only)	Screening	Day -1	Day 1	Day 2	Day 3			D	ay	4			Day 5	Day 6	Day 7	Day 14	Day 21			Da	y 28			End of study	
Study Day(s)	-28 to -4	-1	1	2	3				4				5	6	7	14	21				28			35	65
			-						-						-1 +1	-1 +1	-1 +1		1		+0	ı	1	-1 +2	
Time (post-dose)	-	0h	-			0h	1h	2h	3h	4h	8h	12h			-	-	-	0h	1h	2h	3h	4h	8h	-	
examination																				 	-	ļ			
Alcohol Test, Drug Screen, and Cotinine Test	Х																								
ECG evaluation	Х																							X	
Hematology	Х	Х														Х		Х						Х	
Blood chemistry ⁵	Х	Х	Х	Х	Х				Χ				Х	Х	Х	Х	Х	Х						Х	
Urinalysis	Х	Х	Х	Х	Х				Х				Х	Х	Х	Х	Х	Х						Х	
Corporate Confidential Information	Х	Х	Х	Х	х				Х				Х	х	Х	Х	Х	Х						х	

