**Part 2 will enroll n=72 patients randomized 3:3:2 to LHW090**

Corporate Confidential Information

The study will be conducted in two parts. Part 1 will enroll a single cohort of 12 patients who will be randomized in a 2:1 ratio of LHW090 to placebo. An intra-patient dose escalation scheme will be employed starting at a [redacted] once daily dose for the first four day cycle, and then the dose will be escalated [redacted] once daily for the next four days and then [redacted] once daily for four days. If a renal event occurs during the treatment periods of the study or any of the individual stopping criteria are met, then dosing will be stopped for that individual patient. For the purposes of this study, a renal event will be defined as a reproducible increase from baseline serum creatinine of  $\geq 0.3$  mg/dL confirmed on a repeat measurement within 24-48 hours ([Mehta et al 2007](#), [Khwaja 2012](#)). Throughout the study, any serum creatinine assessment that is increased  $\geq 0.3$  mg/dL compared to baseline will trigger a repeat assessment of serum creatinine after 24 hours to confirm whether criterion for a renal event is met.

Corporate Confidential Information

Part 2 will be double-blind and placebo-controlled to assess the safety and tolerability of 2 dose levels of LHW090, [redacted] once daily for 4 weeks. Approximately 72 patients will be enrolled in Part 2 and randomized in a 3:3:2 ratio to LHW090

[redacted] and placebo. Therefore, in Part 2, approximately 27 patients are expected to be randomized to each of the active doses, and 18 patients are expected to be randomized to placebo. Randomization will be stratified by ARB dose (see Protocol) at the time of enrollment. Patients who meet the eligibility criteria at screening will have baseline assessments of renal function [redacted] collected on Day -1 prior to beginning the treatment phase on Day 1. Centrally-analyzed laboratory assessments performed at screening will be used to determine patient eligibility for the trial.

Corporate Confidential Information

The first 16 patients in Part 2 will be domiciled for the first 7 days of dosing to ensure careful monitoring of renal function and pharmacokinetic parameters. On Day 7 at the investigator's discretion, the patients will be released to complete the remaining 3 weeks of the treatment phase.

Corporate Confidential Information

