## **7 Statistical methods for safety and tolerability data**

### **7.1 Variables**

Corporate Confidential Information

Corporate Confidential Information

The primary safety variable will be the proportion of patients who develop a renal event. The two parts of the study will be analyzed separately. A renal event is defined as a reproducible increase in serum creatinine of  $\geq 0.3$  mg/dL from baseline confirmed on a repeat measurement within 24 to 48 hours.

Change from baseline for serum creatinine will be evaluated and categorized as  $< 0.3$  mg/dL and  $\geq 0.3$  mg/dL. The analysis will be based on central laboratory results. Baseline will be defined as the average of all available pre-dose measurements (excluding screening values).

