## 7.2 Statistical model, assumptions and hypotheses

For Part 2, no inferential analysis of renal events will be conducted due to only having 1 subject that fulfilled the criteria. A frequency table will be produced instead.

Historical data from internal Novartis studies in a similar patient population may be used to supplement the information from patients on placebo in the current study.

For each part, change from baseline for serum creatinine data will be analyzed using a linear mixed effects model for repeated measurements. The model will include treatment as a fixed effect, visit as a repeated effect, treatment by visit interaction and baseline as a continuous covariate. An unstructured covariance model will be used. Point estimates and the associated 95% confidence intervals for the difference between treatment and placebo at each visit will be provided.

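### The unstructured repeated-measures model cannot be fitted to Part 1: 14 post-baseline creatinine visits in 12 patients leave its likelihood without a maximum

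*SAP*

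**What the plan says.** SAP 7.2 covers both parts: "For each part, change from baseline for serum creatinine data will be analyzed using a linear mixed effects model for repeated measurements". The terms are treatment, visit, their interaction, and baseline as a covariate. The covariance is fixed: "An unstructured covariance model will be used". The output is also fixed: "Point estimates and the associated 95% confidence intervals for the difference between treatment and placebo at each visit will be provided". Protocol 11.4.4 gives the same model under supportive analyses.

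On size, SAP 1.4 states "Part 1 will enroll a single cohort of 12 patients who will be randomized in a 2:1 ratio", which is 8 on LHW090 and 4 on placebo. Protocol 11.6 bases that number on feasibility.

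The SAP gives no visit count for Part 1; it has to be read from the schedule. Creatinine is in the chemistry panel (Protocol 8.4.4). Table 8-1 schedules chemistry on Day -1, on each of Days 1 to 14, and at end of study (EOS). A footnote to that table reads "Assessments on Study Days 1-3, 5-7, and 9-11 should be done pre-dose". SAP 7.1 averages the pre-dose values, without screening, to form baseline. Day 1 is therefore part of baseline.

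The visible text gives no reduced visit set, simpler covariance or fallback for Part 1.

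**The concern.** The plan asks for a 14 x 14 unstructured covariance from 12 patients. If the likelihood has no maximum, this is more than a convergence problem: no starting value, optimiser setting or degrees-of-freedom method can supply an estimate. The adjusted differences fail along with their standard errors, because the single baseline slope is shared across visits and its estimate depends on the covariance.

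Two things are at stake. Serum creatinine is a named Part 1 endpoint, and this model is the only Part 1 creatinine comparison with placebo in the visible text that carries a confidence interval. Protocol 11.4.3 also leaves missing creatinine values to the likelihood of the repeated-measures model. If the SAP is silent, the analyst will meet the failure at the first run and choose a substitute with data in hand.

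**Working it through.** The documents give no computed figure for this model, so there is none to reproduce first.

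**Inputs**
- Patients: n = 12, 8 v 4 (SAP 1.4).
- Post-baseline visits (Table 8-1): Days 2-8 (7) + Days 9-14 (6) + EOS (1) = 14.
- Fixed effects: 2 x 14 cell means + 1 baseline slope = 29.
- Covariance parameters: 14 x 15 / 2 = 105.
- Observations if complete: 12 x 14 = 168.

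The 29 + 105 = 134 parameters are fewer than the 168 observations, so the parameter count alone is not the obstacle. The rank is.

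**Step 1: rank.** Removing two arm means at each visit leaves residuals of rank at most n - 2 = 10, whatever the slope. With 14 visits, at least 14 - 10 = 4 directions have zero residual variation. The rank was 10 in 500 of 500 simulated data sets.

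**Step 2: likelihood.** Let eps be the variance assigned to those 4 directions. Each tenfold fall in eps should add:
- ML: 12 x 4 x ln(10) / 2 = 55.3.
- REML: (10 x 4 - 1) x ln(10) / 2 = 44.9, where the -1 is for the slope.

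One simulated 8 v 4 data set gave:

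| eps | ML | REML |
|---|---|---|
| 1e-2 | 211.5 | 140.2 |
| 1e-3 | 266.8 | 185.9 |
| 1e-4 | 322.0 | 231.1 |
| 1e-5 | 377.3 | 276.0 |
| 1e-6 | 432.6 | 320.9 |

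The steps match the formulas, and neither criterion levels off. The same happens without EOS (13 visits) and with Days 2-12 only (11 visits). In a simulated data set with two dropouts and two scattered gaps, REML still rose from 89.4 to 118.8 as eps fell from 1e-2 to 1e-8, so missing values do not rescue the fit.

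**Step 3: where the model becomes estimable.** If n - 2 equals the number of visits T, the determinant of the residual matrix is linear in the common slope, so some slope makes it zero and the likelihood is again unbounded. The condition is therefore T <= n - 3. Twelve patients allow at most 9 visits, and 14 visits need at least 17 patients. In 100 data sets for each case:
- 12 patients/10 visits and 16 patients/14 visits: a singular slope always existed (smallest singular value at most 1e-14).
- 12 patients/9 visits and 17 patients/14 visits: the smallest singular value stayed at or above 2e-4.

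**Step 4: what a by-visit ANCOVA would give.** Residual df = 12 - 3 = 9. The 95% half-width in residual SDs is t(0.975, 9) x sqrt(1/8 + 1/4 + d^2/Sxx), where d is the arm difference in mean baseline and Sxx the within-arm baseline sum of squares.
- Minimum (d = 0): 2.262 x sqrt(0.375) = 1.385.
- Over 200,000 draws with normal baseline: median 1.418, mean 1.464, 95th percentile 1.693.
- One placebo patient missing (8 v 3): 2.306 x sqrt(1/8 + 1/3) = 1.561 at minimum.
- Simulated coverage over 20,000 trials: 94.9% and 95.0% at day-to-day correlations of 0.9 and 0.5.

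**The case against.** The algebra is hard to dispute. The case against rests on context.

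- **Redaction.** Text is blacked out in SAP 7.1, after 7.2.1 (the model-checking section) and in 7.4. A fallback or a shorter visit list could sit there. This stands, and it limits the conclusion to the visible text.
- **The protocol may not need the model in Part 1.** Protocol 11.4.2 plans descriptive statistics for Part 1, and 11.4.4 does not say that the model covers both parts. Much of 11.4.3 turns on two weeks of treatment, whereas Part 1 dosing lasts 12 days. This is fair, but SAP 7.2 applies the model to both parts explicitly, and the SAP is what the analyst follows. It does make confining the model to Part 2 a coherent alternative.
- **Little information is lost.** The model is supportive, the cohort is sized by feasibility, no visible decision rule uses the fit, and intervals with 4 placebo patients would be wide in any case. All true. This limits the importance of the point, but the SAP still promises an output that its named method cannot deliver.
- **Some remedies are untested.** Neither Kenward-Roger df nor a spatial-power structure was simulated. This also stands, and it is one reason to prefer the by-visit ANCOVA.

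**Conclusion.** The concern holds. As visibly written, SAP 7.2 specifies a Part 1 model with no ML or REML maximum: residual rank is at most 10 against 14 visits. The differences and 95% CIs promised for each visit cannot come from it. This follows from the planned numbers and does not depend on the simulated values. It assumes 12 patients, the 14 visits counted from Table 8-1, one common baseline slope, and no fallback in the redacted text.

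The consequence is moderate. The Part 1 creatinine comparison with an interval is lost. The renal-event proportion and descriptive summaries are untouched, and Part 2 is not part of this point. It should be corrected in the SAP.

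**What to change.** Change SAP 7.2 for Part 1 only and leave the Part 2 wording as it is.

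**Preferred.** Analyse change from baseline by a separate ANCOVA at each post-baseline visit, with treatment and baseline as terms, reporting the difference from placebo with a t-based 95% CI (9 residual df with complete data). This gives an estimate at every promised visit and needs no covariance model.

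**Acceptable alternatives**
- (a) Keep the unstructured covariance on a few named visits, for example Days 5, 9, 13 and EOS, with a named small-sample df method such as Kenward-Roger, and describe the other days. A df method matters: in a four-visit REML fit (4,000 trials at each of two correlations), mean coverage was 91.4% and 91.9% with normal quantiles but 94.3% and 94.6% with t on 10 df. Intervals would exist at 4 visits only.
- (b) Use all visits with a named structure based on actual study day, such as spatial power. AR(1) by visit order is unsuitable because EOS falls about 7 days after Day 14. This option rests on a covariance assumption that small-sample df do not protect.

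Limiting the model to Part 2 and describing Part 1 would also remove the inconsistency, but it gives up the interval.

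**Cost.** The change is wording only, but it is post hoc. SAP 7.2 already says of Part 2 that "no inferential analysis of renal events will be conducted due to only having 1 subject that fulfilled the criteria", so the change should be dated and recorded as made after those data were known. ANCOVA uses only patients observed at each visit, so the likelihood-based handling in Protocol 11.4.3 does not carry over. The documents give no residual SD. If it is 0.10-0.20 mg/dL (an assumption), the half-width is at least 0.14-0.28 mg/dL and on average 0.15-0.29 mg/dL, against an event threshold of 0.3 mg/dL.

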Since ARB therapy has been associated with increases in serum creatinine levels, which may be more pronounced in CKD patients; randomization for Part 2 will be stratified by ARB dose--"low" versus "usual" as described in Appendix 2 in order to balance the influence of ARB dose on serum creatinine. A cross-over design was not considered in order to minimize the potential for carry-over effects. A double-blind study was chosen to reduce bias.

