4.2 Inclusion criteria

- 1. Written informed consent must be obtained before any assessment is performed.
 - If consent cannot be expressed in writing, it must be formally documented and witnessed, ideally via an independent trusted witness.
- 2. Male patients and female patients without childbearing potential, age 40 to 85 years of age (inclusive) on a stable (at least 1 month) dose of an angiotensin receptor blocker (ARB) and stable moderately impaired renal function, defined here as an eGFR 30-59 mL/min/1.73m2 (inclusive) using the 4 variable MDRD Study equation for at least 3 months.
- 3. At screening, vital signs (systolic and diastolic blood pressure and pulse rate) will be assessed in the sitting position after the patient has rested for at least five minutes and again after three minutes in the standing position. Sitting vital signs should be within the following ranges:

oral body temperature between 35.0-37.5 °C systolic blood pressure, 100-170 mm Hg diastolic blood pressure, 50-100 mm Hg pulse rate, 50 - 95 bpm

Patients should be excluded if their standing vital signs (relative to sitting) show findings which, in the opinion of the Investigator, are associated with clinical manifestation of postural hypotension (i.e. absence of any other cause). The Investigator should carefully consider enrolling patients with either a > 20 mm Hg decrease in systolic or a > 10 mm Hg decrease in diastolic blood pressure, accompanied by a > 20 bpm increase in heart-rate (comparing standing to sitting results).

- 4. Patients must weigh at least 50 kg to participate in the study, and must have a body mass index (BMI) within the range of $18 - 40 \text{ kg/m}^2$. BMI = Body weight (kg) / [Height (m)]².
- 5. Able to communicate well with the investigator, to understand and comply with the requirements of the study.

4.3 **Exclusion criteria**

- 1. Use of other investigational drugs at the time of enrollment, or within 5 half-lives of enrollment, or until the expected PD effect has returned to baseline, whichever is longer; or longer if required by local regulations.
- 2. History of hypersensitivity to any of the study drugs or to drugs of similar chemical classes.
- 3. History of angioedema, drug-related or otherwise, as reported by the patient.

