6.5 Treatment blinding

This is a sponsor-open, investigator and subject double-blind study: subjects, investigator staff, and persons performing the assessments will remain blind to the identity of study treatments according to the specifications provided in Appendix 1.

The identity of the treatments will be concealed by the use of study drugs that are all identical in packaging, labeling, schedule of administration, appearance, and odor.

Randomization data are kept strictly confidential, and are accessible only to authorized personnel (e.g. unblinded site staff (pharmacist or authorized designee at the site), unblinded sponsor staff (e.g. for drug resupply, unblinded monitor), and sample analysts), until unblinding of the trial as described in the table in the blinding table in Appendix 1.

The study statistician, the study programmer and other personnel involved in data analysis (e.g. biomarker expert) will have access to the randomization list for planned and unplanned interim analyses, and are allowed to share unblinded information with the rest of the clinical team as appropriate for internal decision purposes, as outlined in the blinding table in Appendix 1.

Corporate Confidential Information

Unblinding will occur in the case of patient emergencies (see Section 6.6), at the time of the interim analysis and at the conclusion of the study.

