11.4.2 Statistical model, hypothesis, and method of analysis

Part 1:

The purpose of the dose escalation in Part 1 is to assess the renal safety and tolerability of multiple doses of LHW090 in patients with moderately impaired renal function starting with the highest single dose tested in renal patients in the first-in-human study before the start of Part 2. Descriptive summary statistics will be provided by treatment group and visit/sampling time point, for change from baseline serum creatinine including the frequency (n, %) of renal events <0.3 mg/dL and ≥ 0.3 mg/dL.

Concentration response modeling may be carried out in Part 1 to assess the correlation of change in serum creatinine with concentration. In the absence of a significant concentration effect on serum creatinine, Part 2 will be initiated Corporate Confidential Information If there is evidence of significant concentration effect, Part 2 of the study may not be initiated or a lower dose may be investigated.

Part 2:

For Part 2, a Chi-square test will be performed to compare the proportion of patients who develop a renal event in the LHW090 pooled active doses, LHW090 individual doses and placebo groups. This analysis will be stratified by ARB dose (see Appendix 2). A logistic model with the baseline ARB dose and the baseline creatinine level as covariates may also be used. P-value and 95% CI of the difference in proportions will be presented. Descriptive summary statistics will be provided by treatment and visit/sampling time point, for change from baseline serum creatinine including the frequency (n, %) of renal events <0.3 mg/dL and ≥ 0.3 mg/dL will be provided.

Historical data from internal Novartis studies in a similar patient population may be used to supplement the information from patients on placebo in the current study.

Analyses stratified by degree of proteinuria (microalbuminuria or macroalbuminuria) and/or history of diabetes may also be conducted.

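### Part 2 is randomised within ARB-dose strata, but the creatinine repeated-measures model omits the stratum, so its 95% intervals are too wide to the extent that ARB dose predicts creatinine change beyond baseline

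*SAP*

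**What the plan says.** SAP 1.4 states the allocation method for Part 2: "Randomization will be stratified by ARB dose (see Protocol) at the time of enrollment". Protocol 3.2 gives the reason. ARB therapy has been linked to rises in creatinine, possibly larger ones in chronic kidney disease, so "randomization for Part 2 will be stratified by ARB dose", with levels low and usual, to even out that influence between arms.

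Protocol 11.4.2 carries the stratum into the planned renal-event comparison, which is to be stratified by ARB dose. It adds an option: "A logistic model with the baseline ARB dose and the baseline creatinine level as covariates may also be used".

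SAP 7.2 then withdraws that comparison for Part 2: "no inferential analysis of renal events will be conducted due to only having 1 subject that fulfilled the criteria". A frequency table replaces it. What remains is a repeated-measures model for change from baseline in creatinine, with an unstructured covariance and a 95% interval for each treatment-placebo difference at each visit. Its terms are: "The model will include treatment as a fixed effect, visit as a repeated effect, treatment by visit interaction and baseline as a continuous covariate". Protocol 11.4.4 lists the same terms under supportive analyses. ARB dose appears in neither version.

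**The concern.** Stratified allocation balances the arms on the stratum, which removes between-stratum variation from the sampling error of the treatment contrast. A model without the stratum leaves that variation in its residual. The reported standard error then describes a less precise trial than the one that was run.

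The result is over-wide intervals, with no bias. In a renal-safety study this is not wholly harmless: a wider interval more easily includes zero, so a creatinine rise on drug is harder to see. Placebo is expected to have only 18 patients, so precision is scarce. With renal events reduced to a frequency table, these intervals are the only Part 2 between-group creatinine estimates in the visible SAP.

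**Working it through.** **Plan's own figures.** Neither document gives a precision or power figure for the creatinine model. The only power statement (Protocol 11.6: 82%, 28% against 3%, 54 against 18 patients, one-sided 10%) concerns the renal-event test. A continuity-corrected normal approximation gives 82.7%, so it reproduces, but it does not bear on this point.

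**Inputs from the documents.** Part 2 has about 72 patients allocated 3:3:2, that is 27, 27 and 18 (Protocol 3.1), in two ARB-dose strata (Protocol 3.2).

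**Assumptions.** The documents do not give R², the share of residual variance (after treatment and baseline) that the stratum explains. The visible text also gives no stratum split or block size. R² is therefore shown as a range. The simulation uses splits of 50:50 and 25:75 and blocks of 8.

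**Formula.** Let σ² be the residual variance without the stratum. With allocation balanced within strata:

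- sampling variance of a dose-placebo difference, with or without the term ≈ σ²(1 − R²)(1/27 + 1/18)
- variance reported by the model without the term ≈ σ²(1/27 + 1/18)
- ratio of reported to actual standard error = 1/√(1 − R²)

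The reported interval is what a correctly adjusted trial of 72(1 − R²) patients would give, an apparent loss of 72 × R² patients.

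| Assumed R² | 1/√(1 − R²) | SE inflation | 72 × R² |
|---|---|---|---|
| 0 | 1.000 | 0% | 0 |
| 0.02 | 1.010 | 1.0% | 1.4 |
| 0.05 | 1.026 | 2.6% | 3.6 |
| 0.10 | 1.054 | 5.4% | 7.2 |
| 0.15 | 1.085 | 8.5% | 10.8 |

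**Simulation check.** A single-visit analysis of covariance with complete data stood in for one visit of the planned model (6,000 trials per setting). Paired values are for the 50:50 and 25:75 splits.

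| Assumed R² | Mean width without / with stratum | Coverage without stratum | Coverage with stratum |
|---|---|---|---|
| 0 | 0.999, 0.999 | 94.8%, 95.1% | 94.8%, 95.0% |
| 0.02 | 1.010, 1.010 | 95.3%, 95.3% | 95.2%, 95.0% |
| 0.05 | 1.026, 1.027 | 95.4%, 95.7% | 95.0%, 95.1% |
| 0.10 | 1.055, 1.055 | 95.9%, 96.0% | 94.6%, 95.0% |
| 0.20 | 1.123, 1.122 | 97.0%, 97.3% | 95.0%, 95.3% |

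A separate run of 5,000 trials per setting, with strata of 32/40 and 16/56, gave a width ratio of 1.09 at R² = 0.15 and coverage of 96.6–96.9% without the stratum.

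**Where the excess width comes from.** At R² = 0.20 with a 50:50 split, the sampling SD of the estimate was 0.307 without the term and 0.305 with it (units: residual SD within stratum), so the design had already delivered the precision. With unstratified allocation at the same R², the model without the stratum had a sampling SD of 0.344 and correct coverage of 95.0%. The excess width therefore comes from stratifying and then not adjusting.

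**Cost if the stratum is irrelevant.** Residual degrees of freedom fall from 68 to 67, and the 97.5% t quantile moves from 1.9955 to 1.9960, a ratio of 1.0003. Including chance imbalance, the simulated intervals widened by less than 0.1% at R² = 0.

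**The case against.** The strongest reply is that no actual loss has been shown. R² is unknown and may be close to zero. Protocol 4.2 requires at least one month on a stable ARB dose, the outcome is change from baseline, and baseline creatinine is a covariate. Protocol 3.2 links ARB therapy to creatinine level and does not say that ARB dose predicts later change. At R² of 0 to 5%, the intervals are only 0 to 2.6% too wide. This stands and is why the finding is conditional. It does not settle the matter, since baseline creatinine need not capture how creatinine responds to study drug under different ARB doses.

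The error is also conservative, the model is labelled supportive in the protocol, no margin or alpha attaches to it, and the SAP matches the protocol. All true. These points limit the importance without making the omission right.

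Changing a pre-specified model now is a real cost. The SAP already cites an observed event count, and Protocol 6.5 says: "This is a sponsor-open, investigator and subject double-blind study". Reporting both models and dating the change answers this.

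The simulations used one visit, and a main effect recovers the full gain only if the stratum effect is constant over visits. A large-sample calculation (six visits, assumed correlations 0.5–0.7, equal strata, R² 10% at Day 28) gave a Day 28 gain of 5.4% for a constant effect and 3.5–5.0% for a varying one. That trims the benefit modestly.

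Finally, parts of the SAP are redacted and Protocol Appendix 2 is not visible, so use of ARB dose in hidden text cannot be excluded.

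**Conclusion.** The concern holds in its conditional form. In the visible text, Part 2 is randomised within ARB-dose strata and its one remaining between-group creatinine model ignores them. Point estimates are unbiased. Intervals are too wide by 1/√(1 − R²): nothing at R² = 0, about 1 to 5% for R² of 2 to 10%, and 8.5% at 15%. The documents cannot place the trial within that range, and the lower end is quite plausible. The figures rest on the assumed R², two strata, balanced allocation within strata and a single-visit stand-in for the repeated-measures model. The change is worth making because the direction of the error is known and the correction is nearly free. Leaving it out would not invalidate the analysis.

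**What to change.** In SAP 7.2, add ARB-dose stratum as randomised (low or usual) as a fixed main effect in the Part 2 creatinine model. A stratum-by-visit term is not needed. Leave the Part 1 model as it is, since stratification applied only to Part 2. Report the currently specified Part 2 model as a sensitivity analysis. Label the added term as a departure from Protocol 11.4.4, and state when it was decided relative to unblinding and to knowledge of the event count.

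The cost is one degree of freedom, one extra model run and a sentence or two in the SAP. No new data are needed, because the stratum is fixed at randomisation.
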